6.9. Assessment of Study Subject Clinical Course

Assessment of study subject signs, symptoms and daily clinical course will be conducted regularly, as specified in [Table 6-1](#). These will include (and are not limited to):

- Daily recording of subjects' overall Clinical Status, from most severe to least severe, using a categorical scale similar to the ordinal scale of Clinical Status being used in the NIAID controlled trial design for comparatively assessing parallel study arms for treating COVID-19 patients (NCT04280705). From most severe disease to progressively less severe disease, the stages of this adapted ordinal scale of overall Clinical Status are defined as follows:

1. Death
2. Hospitalized, on invasive mechanical ventilation or ECMO
3. Hospitalized, on non-invasive ventilation or high flow oxygen devices
4. Hospitalized, requiring supplemental oxygen
5. Hospitalized, not requiring supplemental oxygen – requiring ongoing medical care (COVID-19 related or otherwise)
6. Hospitalized, not requiring supplemental oxygen – no longer requires close medical care for COVID-19

(Note: Examples include recovered subjects needing inpatient quarantining/confinement or needing social services connections for outpatient living.)

7. Not hospitalized, but with limitation on activities and needing close outpatient care for COVID-19 manifestations
8. Not hospitalized, no limitations on activities, no need for continued close medical care

Protocol Number: AT-03A-001

Subjects with Status 2 or 3 disease at Screening would not be eligible for the study, but enrolled subjects who progress to respiratory failure/mechanical ventilation during the study will have deteriorated to Status 2 on this scale. It is anticipated that most “moderate” COVID-19 patients eligible for this study will be enrolled with an overall Clinical Status of 4 or 5. During the study, subjects’ overall Clinical Status may worsen or improve. Maximal deteriorations will be to Status 1 (death). Deterioration to Status 2, corresponding to respiratory failure/mechanical ventilation, would require the subject to be discontinued from study treatment, and the subject would thereby be eligible for treatment with any therapies appropriate for severe COVID-19. Subjects will have achieved the secondary endpoint of “clinical recovery” with improvement to Status 6, 7 or 8.

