8.2. Endpoints

8.2.1. Primary Efficacy Endpoint and Sample Size Calculations

Part A

The primary endpoint for Part A of this study is the proportion of subjects with PRI, defined as a ≥ 2 -tier increase in respiratory support methods required to maintain satisfactory oxygenation ($\text{SpO}_2 \geq 93\%$), using the 6-tier hierarchical scale of Respiratory Support methods described in **Section 6.9**.

The primary efficacy goal is to reduce the incidence of PRI by 50% for active-dosed subjects compared to placebo recipients. The featured timeframe for this primary endpoint analysis will be the 14-day primary study period, with secondary analyses at study Days 10, 21, and 28.

With this study's relatively high-risk COVID-19 subject population (one or more known risk factors for poor outcomes), the study postulate is that 40% of placebo recipients will experience PRI during the 14-day study period, and the efficacy goal is therefore to reduce that incidence of PRI to 20% or less in active recipients.

Assuming PRI rates (PRIR) of 0.4 and 0.2 in the control and experimental arms, respectively, at alpha one-sided of 0.025, and at a power of 0.8, a total of 182 subjects are required at a 1:1 allocation, i.e. 91 per study arm. The study statistical hypotheses are as follows:

$$H_0: \text{Experimental}_{\text{PRIR}} \geq \text{Control}_{\text{PRIR}}$$

$$H_a: \text{Experimental}_{\text{PRIR}} < \text{Control}_{\text{PRIR}}$$

Part B

The primary endpoint of Part B is the change from baseline in amount of SARS-CoV-2 virus RNA (viral load) as measured by RT-PCR. Viral load will be assessed quantitatively using a validated assay. Analyses will be carried out at each scheduled time point using the mITT population. Part B of the study is signal seeking. The primary analysis aims to identify and characterize any potential effect of AT-527 on viral load over time. Analyses and p-values are descriptive and no adjustment for multiple comparisons will be made.

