8.3. Efficacy Analysis Methods

8.3.1. Primary Efficacy Analysis

Part A

The ITT population will be the primary efficacy analysis population for Part A. Proportions of subjects (active or placebo-treated) with PRI until study completion (Day 14) will be compared by study arm. The Cochran Mantel Haenszel (CMH) test will be performed to compare the proportion of PRI rate in study arms. Stratification variables will include the randomization strata of geographic regions; additional stratification variables may be described in the eventual SAP, to be finalized prior to database lock.

Part B

Viral load will be assessed quantitatively using a validated assay. The analyses will compare change from baseline log10 viral load at each required scheduled timepoint. The analyses will be carried out on the mITT population. Change from baseline viral load will be compared between the AT-527 group and the placebo group at required post-baseline timepoint using ANCOVA with treatment as a factor and log10 baseline viral load as a covariate. The least squares mean (LSM) change and its standard error of means (SE) in each group, the differences between two groups in LSM change with corresponding 95% confidence intervals (CIs), and p-values will be presented.

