13. APPENDIX

Appendix 1 (Applicable to Part A only)

Sample Size Code:

Primary Endpoint (SAS):

```
proc power; twosamplefreq test=fisher  
groupproportions = (.2 .4) ntotal = . power = .8; run;
```

First Key Secondary Endpoint (R):

```
p nsim <- 10000  
pwil <- rep(NA,nsim)  
set.seed(837820122)  
for (i in 1:nsim) {  
  y0 <- rexp(91,log(2)/7)  
  y1 <- rexp(91,log(2)/12)  
  ydf <- data.frame(yt=c(y0,y1),trt=rep(0:1,c(91,91)))  
  ydf$yobs <- ifelse(ydf$yt>14,15,ceiling(ydf$yt))  
  pwil[i] <- wilcox.test(ydf$yobs[ydf$trt==0],ydf$yobs[ydf$trt==1],alternative="less")$p.value  
}  

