## 7.6. ADJUSTMENTS FOR COVARIATES AND FACTORS TO BE INCLUDED IN ANALYSES

The analyses will be adjusted for the following covariates and factors.

- Geographic regions (stratification variable for randomization)
  - North America
  - South America
  - Europe
  - Rest of World
- Baseline quantitative SARS-CoV-2 (virologic endpoints only)

If data are too sparse for one level of the Geographic region factor (i.e., less than 5% of subjects), South America and Rest of World will be combined. If the level is still less than 5% of subjects, then the factor will not be included in the statistical model/test. Determination of the factor(s) to be included into the statistical models/tests will be finalized before the study DBL in a blinded fashion.

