### 16.1. PRIMARY EFFICACY

#### 16.1.1. PRIMARY EFFICACY ENDPOINT

The primary endpoint for this study is the proportion of subjects with PRI on or before Day 14. The PRI is defined as a  $\geq$  2-tier increase from baseline in respiratory support methods required to maintain satisfactory oxygenation ( $\text{SpO}_2 \geq 93\%$ ), using the 6-tier hierarchical scale of Respiratory Support methods which have the following levels:

- LEVEL 1: Normal oxygenation on room air ( $\text{SpO}_2 \geq 93$ ), no need for supplemental  $\text{O}_2$
- LEVEL 2: Persistent hypoxemia on room air ( $\text{SpO}_2 < 93$ ) with requirement for low-level supplemental  $\text{O}_2$  by nasal cannula or mask (up to 2L/min) to maintain  $\text{SpO}_2 \geq 93$
- LEVEL 3: Requirement for higher levels of passive supplemental  $\text{O}_2$  by nasal cannula or mask ( $\geq 2\text{L/min}$ ) to maintain  $\text{SpO}_2 \geq 93$
- LEVEL 4: Requirement for oxygenation by positive-pressure devices, e.g. Continuous Positive Airway Pressure (CPAP) or Bi-level Positive Airway Pressure (BiPAP) or other non-invasive positive-pressure respiratory support methods to maintain satisfactory oxygenation and/or ventilation
- LEVEL 5: Requires invasive respiratory support (intubated mechanical ventilation or ECMO)
- LEVEL 6: Death

The assessment scores of respiratory support level are collected on the Ordinal Scale of Respiratory Support Level

Document: \[REDACTED]\net\enterprise\Apps\sasdata\SASb\SAS\Atea\_Pharmaceuticals\AT-527\ISZA63631\Biostatistics\Documentation\SAP\AT-03A-001\_V1.0\_COVID\_SAP\_PA7.doc  
Author: \[REDACTED] Version Number: V1.0  
Template No.: CS\_TP\_BS016 Revision 6 Version Date: 15Apr2021  
Effective Date: 02Dec2019 Reference: CS\_WI\_BS005

Copyright © 2009, 2010, 2012, 2016, 2018, 2019 \[REDACTED] All rights reserved. The contents of this document are confidential and proprietary to \[REDACTED] Holdings Inc. and its subsidiaries. Unauthorized use, disclosure or reproduction is strictly prohibited.

page of the eCRF (electronic Case Report Form).

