The analyses will compare change from baseline log10 quantitative SARS-CoV-2 at each required scheduled timepoint. Any missing data will not be included in the analyses. Change from baseline quantitative SARS-CoV-2 will be compared between the AT-527 group and the placebo group at each of days 2, 5, and 14 using ANCOVA with treatment as a factor and log10 baseline quantitative SARS-CoV-2 as a covariate. For each time point and LOQ handling method, the least squares mean (LSM) change and its standard error of means (SE) in each group, the differences between two groups in LSM change with corresponding 95% confidence intervals (CIs), and p-values will be presented. Statistical significance at Day 2 and Day 5 will be assessed based on two-sided 0.025 level test to account for 2 comparisons. The formal statistical comparison will be based on Method 1.

The raw and LSMs change from baseline in log10 will also be presented graphically over time.

#### 16.2.4.2. Time to Clinical Recovery (days) by Day 14

Another key secondary efficacy goal is to shorten the median days to clinical recovery (MDCR) by at least 4 days for active-dosed subjects compared to placebo recipients during the 14-day primary study period. The median times

Document: \[REDACTED]\net\enterprise\Apps\sasdata\SASb\SAS\Atea\_Pharmaceuticals\AT-527\5ZA63631\Biostatistics\Documentation\SAP\AT-03A-001\_V1.0\_COVID\_SAP\_PA7.doc  
Author: \[REDACTED] Version Number: V1.0  
Template No.: CS\_TP\_BS016 Revision 6 Version Date: 15Apr2021  
Effective Date: 02Dec2019 Reference: CS\_WI\_BS005

Copyright © 2009, 2010, 2012, 2016, 2018, 2019 \[REDACTED] All rights reserved. The contents of this document are confidential and proprietary to \[REDACTED] Holdings Inc. and its subsidiaries. Unauthorized use, disclosure or reproduction is strictly prohibited.

to clinical recovery will be presented for each treatment group as well as the number and percentage of subjects with and without clinical recovery. The Wilcoxon Mann-Whitney test will be used to test that there is no difference between the treatment groups by a one-sided  $\alpha=0.025$  p-value.

As a sensitivity analysis a Kaplan-Meier curves (product-limit estimate) will be provided by treatment arm for the time to clinical recovery (days). Subjects will be censored as follows:

- If subject dies without clinical recovery, censor at Day 15
- If subject has no post-baseline scale, censor at Day 1

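### Time to clinical recovery is tested without stratifying by entry Clinical Status, although subjects are expected to start at two different distances from the recovery threshold

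*Protocol*

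**What the plan says.** Protocol 6.9 expects most patients "eligible for this study will be enrolled with an overall Clinical Status of 4 or 5". On its scale, Status 4 is in hospital on supplemental oxygen, and Status 5 is in hospital without oxygen but still needing care. SAP 16.2.1.2 defines recovery as the first score of 6 or above and assigns 15 days to anyone not recovered by Day 14. SAP 16.2.4.2 gives the analysis: "The Wilcoxon Mann-Whitney test will be used to test that there is no difference between the treatment groups", with no strata named.

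Randomisation is stratified by region only (protocol section 8). SAP 7.6 lists two adjustment factors: region, and "Baseline quantitative SARS-CoV-2 (virologic endpoints only"). SAP 10 reports the entry Clinical Status Score descriptively, and it is not among the subgroups in SAP 7.7. Protocol 8.3.1 said, for the PRI test, that "additional stratification variables may be described in the eventual SAP". The SAP added none for clinical endpoints, and the March 2022 changes form adds none either.

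PRI is defined differently, as a "2-tier increase from baseline in respiratory support methods required to maintain satisfactory oxygenation" of at least that size. It is tested by CMH controlling for region (SAP 16.1.3).

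**The concern.** A subject entering at Status 4 must come off oxygen and also cease to need close care. A subject entering at Status 5 needs only the second. If natural recovery times differ between these groups, ranking everyone together adds the between-group spread to the noise in the treatment comparison. That noise can be removed with a variable already recorded before dosing.

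There are two consequences. Power falls below what the same patients could give. And if one arm happens to receive more Status 5 subjects, nothing in the planned test corrects for it. The second matters more in a small trial, and Part A closed at 81 randomised subjects.

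**Working it through.** **Inputs from the documents.** Exponential recovery times, median 12 days on placebo and 7 on active, 91 per arm, one-sided 0.025, 80% power (SAP 7.1). Times are rounded up to whole days and set to 15 if beyond Day 14 (protocol Appendix 1). Part A randomised 81 (protocol 3.1).

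**Assumptions not in the documents.** Half the subjects enter at each status. Status 5 subjects recover *r* times as fast as Status 4 subjects, with *r* = 1, 2 or 3.

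**Step 1: reproduce the plan's figure.** Expected recoveries by Day 14 are 91 × (1 − 0.5^(14/12)) = 50.5 on placebo and 91 × (1 − 0.5^(14/7)) = 68.3 on active. The SAP states about 50 and 68. Rebuilding the appendix simulation (10,000 trials) gives Wilcoxon power of 80.0%. The stated figure is correct under its own assumption of one exponential distribution per arm.

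**Step 2: allow mixed entry severity and keep the medians.** Write *x* for the probability that a Status 4 placebo subject is unrecovered at day 12. A placebo median of 12 requires 0.5*x* + 0.5*x*^r = 0.5.

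- *r* = 2: *x* = 0.618, Status 4 rate = −ln(0.618)/12 = 0.0401 per day.
- *r* = 3: *x* = 0.682, Status 4 rate = 0.0319 per day.

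Multiplying every rate by 12/7 on active scales all times by 7/12, so the active median stays at 7.

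**Step 3: compare the tests.** The van Elteren statistic is Z = Σ w_k(W_k − E_k) / √(Σ w_k² V_k). Here W_k is the active rank sum in stratum k, E_k and V_k are its null mean and tie-corrected variance, and w_k = 1/(N_k + 1). Separate runs of 5,000 to 8,000 trials per setting gave:

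| Per arm | r | Wilcoxon power | Stratified power | Gain (points) |
|---|---|---|---|---|
| 91 | 1 | 80–81% | 80% | 0 to −1 |
| 91 | 2 | 76–77% | 78–79% | about 2–3 |
| 91 | 3 | 71% | 77–78% | about 6–7 |
| 40 | 2 | 42–43% | 44% | about 2 |
| 40 | 3 | 37–39% | 41–43% | about 4 |

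Under the null, one-sided rejection stayed near 0.025 for both tests.

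**Step 4: size of a chance imbalance.** With arms of 40 and 41, the SD of the between-arm difference in the Status 5 share is √(0.25 × (1/40 + 1/41)) = 0.111. By Day 14 the two placebo groups differ in recovery by 0.570 − 0.325 = 0.245 (*r* = 2) or 0.640 − 0.262 = 0.378 (*r* = 3). A one-SD imbalance therefore moves the Day 14 difference by 0.111 × 0.245 = 2.7 points or 0.111 × 0.378 = 4.2 points with no drug effect. The standard error of that difference is also about 11 points when rates are near 50%, so the shift is roughly a quarter to two fifths of a standard error.

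At 91 per arm, an imbalance of about 9 to 13 points favouring active occurs in 5 to 6% of trials. Given that, the unstratified false-positive rate was about 0.04 at *r* = 2 to 3, against about 0.02 stratified. These rest on some 350 runs each and are imprecise.

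**Step 5: PRI.** The plan's figure is "Assuming PRI rates (PRIR) of 0.4 and 0.2 in the control and experimental arms", "at alpha one-sided of 0.025, and at a power of 0.8, a total of 182 subjects are required at a 1:1 allocation". The appendix code is "proc power; twosamplefreq test=fisher". The continuity-corrected formula returns 91 per arm, and exact Fisher power at 91 is 0.808, so 182 reproduces. Adding entry level to CMH at these rates gains 0 to 0.5 points up to an odds ratio of 2, and just under 4 points at an odds ratio of 5. At assumed low rates of 0.10 versus 0.05, power at 91 per arm is 0.24 unstratified versus 0.24 to 0.25 stratified. At 40 per arm it drops from 0.14 to 0.12.

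**The case against.** The strongest reply is that nothing here is an error. Protocol 8.3.1 permits further strata but does not require them, and both stated powers reproduce. The entry mix and prognostic strength are the reviewer's assumptions; at 2-fold the gain is only about 2 points. Part A stopped at 81 subjects, and after Amendment 8 the protocol treats all analyses as descriptive. All of that stands, and it limits the weight of the point. It does not remove the case for a nearly free gain in precision on recovery, one of the few clinical outputs the 2022 form retains. That form also drops the Kaplan-Meier sensitivity analysis of recovery.

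A reader might infer four stronger claims that the documents do not support.

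- **Recovery is a change from entry level.** It is a fixed threshold; only PRI is relative to baseline.
- **Imbalance invalidates the test.** Randomisation keeps overall type I error near 0.025. Distortion arises only when an imbalance has occurred.
- **The primary PRI test should be restratified.** Its definition already builds in the starting tier: Level 1 must reach 3 and Level 2 must reach 4. Any remaining prognostic effect is therefore of unknown direction. Protocol 1.1 also describes too few progression events to measure an effect.
- **Respiratory failure or death and the Part B summaries need the same change.** The 2022 form no longer presents the former and only lists Part B patients.

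**Conclusion.** The point holds for time to clinical recovery, as an efficiency and robustness improvement rather than a fault that invalidates the analysis. With mixed entry severity, the stated 80% recovery power would be about 76% at 2-fold and 71% at 3-fold prognostic strength. Stratifying recovers about half of the first loss or more, and about two thirds of the second. These figures depend on the 50:50 mix, exponential times and an equal relative drug effect in both entry groups. If entry status does not predict recovery, there is nothing to gain. For PRI, the evidence supports no more than a sensitivity analysis.

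**What to change.** - **SAP 7.6:** add baseline NIAID Clinical Status (4 or below versus 5 or above) as a factor for the recovery endpoint. Apply the section's existing rule that a factor is dropped when a level holds under 5% of subjects.
- **SAP 16.2.4.2:** replace the unstratified Wilcoxon with a van Elteren test by that factor. Show median times by entry status alongside the overall medians.
- **SAP 16.1.4:** add one sensitivity CMH analysis of PRI by baseline Respiratory Support level (1 versus 2), with a stated rule for pooling sparse strata. Leave the primary CMH test as it is.

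The 2022 form says the SAP itself will not be updated. If that stands, the change can be recorded on that form, with the stratified recovery result shown beside the planned one. It should be labelled as added after Part A results were seen at treatment-group level.

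The cost is SAP wording and one stratum in the code, with no new data. The statistical cost is about 1 point of power at most, if entry status is not prognostic.

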6.10. Sparse PK Sampling

PK samples will be collected, as specified in [Table 6-1](#), at the same time a blood sample is drawn for safety laboratory analysis. It is important that the date and time of the PK sampling is

Protocol Number: AT-03A-001

recorded as well as the date and time of study drug administration. The sparse sampling schedule is to limit exposure of site staff to subjects with COVID-19 as well as to limit workload.

6.10.1. Sample Processing, Storage and Shipping

All PK samples will be processed, stored, and shipped according to the sample processing instructions supplied by the Sponsor or receiving laboratory.

6.10.2. Bioanalytical Methods for PK samples

Plasma concentrations of AT-527 and metabolites (as appropriate) will be measured according to validated bioanalytical methods.

Samples from all subjects who received at least one dose of AT-527 will be analyzed. Samples from subjects who received placebo will not be analyzed.

Bioanalytical laboratory personnel will have access to the randomization assignment. The bioanalytical facility will preserve the blind by reassigning alternative subject numbers for any interim data reviews.

Protocol Number: AT-03A-001

7. ADVERSE EVENTS

7.1. Definitions

An AE is defined as any untoward medical occurrence in a subject administered a medicinal product(s) and which does not necessarily have to have a causal relationship with this treatment. An AE can therefore be any unfavorable and unintended sign (for example, an abnormal laboratory finding), symptom, or disease temporally associated with the use of a medicinal product(s), whether or not considered related to this medicinal product(s).

A suspected adverse reaction is any AE for which there is a reasonable possibility that the drug(s) caused the AE. 'Reasonable possibility' means there is evidence to suggest a causal relationship between the drug(s) and the AE. A suspected adverse reaction implies a lesser degree of certainty about causality than adverse reaction, which means any AE caused by a drug(s).

An AE may be:

- A new illness,
- Worsening of a previous chronic illness or a concomitant illness,
- An apparent adverse effect of the study medication(s) on safety-related laboratory tests. This observation could include a clinically-significant abnormal laboratory value or a significant shift from baseline (though still within normal range) which the clinical investigator or qualified designate considers to be clinically significant.

Surgical procedures themselves are not AEs. They are therapeutic measures for conditions that required surgery. The condition for which the surgery is required is an AE, if it occurs or is detected during the study period. Planned (elective) surgical measures and the conditions(s) leading to these measures are not AEs, if the condition(s) was (were) known before the start of study treatment. In the latter case, the condition should be reported as medical history.

A serious adverse event (SAE) or reaction is any untoward medical occurrence that at any dose:

- Results in death,
- Is life-threatening,
- Requires inpatient hospitalization or prolongation of existing hospitalization,
- Results in persistent or significant disability or incapacity (defined as a substantial disruption of a person's ability to conduct normal life functions),
- Is a congenital anomaly or birth defect,
- Is an important medical event that may jeopardize the subject or may require intervention to prevent one of the other outcomes listed above (according to medical judgment of the qualified investigator).

Laboratory abnormalities without clinical significance are not recorded as AEs or SAEs. However, laboratory abnormalities (eg, clinical chemistry, hematology, and urinalysis) that require medical or surgical intervention or lead to study drug interruption, modification, or discontinuation must be recorded as an AE, as well as an SAE, if they meet the definition above. In addition, laboratory or other abnormal assessments (eg, electrocardiogram, x-rays, vital signs)

Protocol Number: AT-03A-001

that are associated with signs and/or symptoms must be recorded as an AE or SAE if they meet the definition of an AE or SAE as described above. If the laboratory abnormality is part of a syndrome, record the syndrome or diagnosis (eg, anemia), not the laboratory result (ie, decreased hemoglobin). Laboratory abnormalities that do not require medical intervention or action are generally not considered AEs.

Severity should be recorded and graded according to the Division of AIDS (DAIDS) Table for Grading the Severity of Adult and Pediatric Adverse Events, Version 2.1 dated July 2017, as described below. For AEs associated with laboratory abnormalities, the event should be graded on the basis of the clinical severity in the context of the underlying conditions; this may or may not be in agreement with the grading of the laboratory abnormality.

